### **Inclusion/Exclusion Criteria**

### 1. List the criteria for inclusion

Surgical Subjects:

- Age 18+
- Patient scheduled to undergo elective orthopaedic surgical procedure with a minimum anticipated incision length of 3 cm.
- Willingness and ability to comply with scheduled visits and study procedures.

Clinicians:

Version Date: 07-29-22 Page Number: 2 of 8

- Attending surgeons, physician assistants and trainees (fellows and residents) in the orthopaedic surgery department
- Willingness to comply with randomization and study protocols

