# **Statistical Considerations**

# **1.** Is stratification/randomization involved? YES

# ► IF YES, describe the stratification/ randomization scheme.

Simple randomization will be used. A random number generator will be used to devise a list to assign study numbers to treatment groups, ensuring that there will be equal numbers assigned to each group. No other variables will be used for stratification. For each study number, the treatment assignment will be placed into an envelope by the clinical trials coordinator and sealed.

There will be no blinding of subjects or personnel involved in the study once the envelope with group assignment has been opened.

The statistician doing the randomization and the clinical trial coordinator will be the only ones with access to the master treatment assignment list.

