# 7. Will data from multiple sites be combined during analysis? NO

# **Study Procedures-Biomedical Research**

### 1. What will be done in this protocol?

Patients who meet above inclusion criteria and provide informed consent will be enrolled in the study. All members of the research team that will be assisting with the surgical closure (including attending surgeons, fellows, residents and/or physician assistants) will receive full training in the application of both the Clozex and Zipline devices to insure uniform experience among participants. The clinicians performing the closure are also investigators in this research and may opt out of participating in this study. There are no pre-operative study procedures for the patients, aside from a review of inclusion and exclusion criteria and enrollment.

On the day of surgery, the enrolled subject will be randomized into one of three study groups. The randomization will occur during surgery, prior to wound closure. The circulating nurse will open an envelope, which will determine the randomization group for the subject. This will allow operating room staff the time to assemble the appropriate materials for closure depending on participant's group assignment without any delay to standard of care. The subjects' randomization into a treatment group is not expected to significantly increase the time of the operation or duration of anesthesia. The wound closure will proceed as follows:

- 1. Any deep fascial layers will be closed with braided Vicryl suture as indicated and according to standard of care.
- 2. The subcutaneous fat will be closed using 3-0 Monocryl in inverted, interrupted fashion according to standard of care.
- 3. The circulator will then start a timer that will run until the wound is completely closed.
  - A. If randomized to the **Control group**: Closure will proceed with a running 3-0 Prolene subcuticular suture with escape stitches.
  - B. If randomized to the **Clozex treatment group**: Closure will proceed with application of the adhesive device according to manufacturer's recommendations
  - C. If randomized to the **Zipline treatment group**: Closure will proceed with application of the adhesive device according to manufacturer's recommendations

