- 4. If at any time, the surgical provider (attending surgeon, fellow, resident, PA) determines that the device in the test group has failed (i.e. adhesive failure, device breakage), s/he may elect to proceed with suture closure and study cross over shall be recorded.
- 5. At the conclusion of the wound closure, the timer will be stopped and the operative time will be recorded.

Version Date: 07-29-22 Page Number: 5 of 8

Dressings will then be applied in standard fashion including 4 x 4 gauze, webril wrap and ACE bandage and splinting as indicated. The team member who performed the wound closure (attending surgeon, fellow, resident or PA) will fill out the survey on satisfaction with the closure (scale 1 - 10) and note any complications or confounding factors (challenging incision pattern or application problems). The subject will be discharged with standard wound care instructions to keep the surgical dressing in place for 3 days and then to replace it with clean sterile dressings. The subjects will be cautioned not to submerge their wound underwater for at least 2 weeks following surgery, as per standard protocol.

Initial follow up will occur at a standard time interval within 14 - 17 days after surgery, at which point Prolene sutures will be cut and removed and Clozex/Zipline devices will be removed. An assessment of the wound will take place by the same attending surgeon who performed the procedure using the Stony Brook Scar Evaluation Scale (SBSES) using the below rubric (scale 0 - 5).

| Category                 |   | Points |
|--------------------------|---|--------|
| Width                    | > 2 mm  | 0      |
|                          | ≤ 2 mm  | 1      |
| Height                   | Elevated/ depressed in relation to surrounding skin | 0      |
|                          | Flat  | 1      |
| Color                    | Darker than surrounding skin                        | 0      |
|                          | Same color or lighter than surrounding skin         | 1      |
| Hatch marks/Suture marks | Present   | 0      |
|                          | Absent  | 1      |
| Overall appearance       | Poor  | 0      |
|                          | Good  | 1      |
|                          |   |        |

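### The skin closer, who also rates physician satisfaction, need not be designated before the envelope is opened, so closer grade could differ by arm

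*Combined protocol and SAP*

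**What the plan says.** Study Procedures, item 1, places the allocation inside the operation: "The randomization will occur during surgery, prior to wound closure". It also says how the arm becomes known: "The circulating nurse will open an envelope, which will determine the randomization group for the subject". The randomisation text under Statistical Considerations, item 1, adds: "There will be no blinding of subjects or personnel involved in the study once the envelope with group assignment has been opened".

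The deep and subcutaneous layers are then sutured in the same way in every arm. The timed skin step follows, and it is the only step that differs by arm. Attendings, fellows, residents and PAs may all take part in closure. On the rating, the procedures say: "The team member who performed the wound closure (attending surgeon, fellow, resident or PA) will fill out the survey on satisfaction with the closure".

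Three provisions bear on the closers. They "will receive full training in the application of both the Clozex and Zipline devices to insure uniform experience among participants". The inclusion criteria for clinicians require: "Willingness to comply with randomization and study protocols". And: "The clinicians performing the closure are also investigators in this research and may opt out of participating in this study".

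Randomisation is not stratified. Statistical Considerations, item 5, compares physician satisfaction and cost between groups by one-way ANOVA, with no term for operator or grade. Cost is closure time multiplied by the operating room cost per minute, plus materials.

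**The concern.** Randomising patients balances the patients. It does not balance the operator or the rater if either can be settled once the arm is known. Here one person is both, may be of any of four grades, and need not be designated before the envelope is opened. A team could, without breaking any written rule, give an adhesive application to one grade and a running subcuticular suture to another.

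If that happened, a difference in physician satisfaction or closure time could partly reflect who closed and not what was used. Whatever reached closure time would pass into cost through the per-minute multiplier. The planned ANOVA could not separate the two. The protocol also does not ask for the closer's grade to be recorded, so an imbalance might not be seen.

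**Working it through.** **1. The plan's own figures.** The plan gives no figure for physician satisfaction, closure time or grade mix. Its only sample-size figure is 10 per group, for a 1-point SBSES difference with SD 0.73, alpha 0.05 and power 0.80. A two-group comparison reproduces 10. A three-group ANOVA gives 12 with means 0, 0.5, 1 and 9 with means 0, 0, 1. The present point does not rest on this figure.

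**2. The order of events.** Envelope opened, arm known to all, two layers sutured identically, skin step by arm, closer completes the survey. For each provision that might fix the closer beforehand:
- Training covers the two devices. It does not cover the control arm's suture, and it does not say who closes a given case.
- Willingness to comply binds a clinician to the arm drawn. It does not bind the team to a clinician.
- The opt-out has no deadline relative to the envelope.
- The survey's note of complications or confounders gives incision pattern and application problems as examples, not grade.

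None of them designates the closer before the arm is known.

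**3. Size of a spurious difference.** The documents supply no inputs, so these are assumptions. Let p be the share of cases closed by the junior grade, and g the junior-minus-senior difference in mean outcome. The two device arms are pooled for simplicity. With identical techniques:

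spurious difference = (p in device arms − p in suture arm) × g

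- Shares 70% and 40%, g = 2 points or 2 minutes: (0.7 − 0.4) × 2 = 0.6.
- Shares 90% and 30%, same g: (0.9 − 0.3) × 2 = 1.2.

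The sign follows the assumptions. If juniors are 2 minutes slower, the first case adds 0.6 minutes to the device arms and hides that much of a real saving. If juniors rate 2 points higher, it adds 0.6 points to device satisfaction. Reversing the shares reverses both. In cost, 0.6 minutes becomes 0.6 times the operating room cost per minute, which is not given.

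**4. Effect on the three-arm ANOVA.** This was simulated with 40,000 runs per scenario and no true technique effect. The grade effect is in within-grade SDs. The sizes are 10 per arm (the analysis target) and 20 per arm (the enrolment ceiling per group in the sample-size section).

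| Senior-closer share by arm | Grade effect (SD) | Bias (SD) | False positives, 10 per arm | False positives, 20 per arm |
|---|---|---|---|---|
| 50/50/50% | 0.5 to 1.5 | 0 | about 5% | about 5% |
| 70/40/40% | 0.5 to 1.5 | 0.15 to 0.45 | 6 to 12% | 7 to 20% |
| 80/30/30% | 0.5 to 1.5 | 0.25 to 0.75 | 8 to 27% | 11 to 50% |

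Bias is the grade effect times the gap in shares, for example 1.5 × (0.7 − 0.4) = 0.45. It does not shrink with more patients, so the false-positive rate rises with sample size.

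**5. What designating the closer achieves.** Grade mix can then no longer depend on the arm, and the false-positive rate returns to about 5%. Chance imbalance remains. With an assumed 50% senior closers, the largest gap between any two arms is at least 40 percentage points in about 26% of trials at 10 per arm, and in about 4% at 20 per arm.

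**The case against.** The strongest reply is that the documents are silent on when the closer is chosen, and silence is not evidence of selection. The text speaks of a single team member who performed the closure. That reads more naturally as one person closing throughout than as a hand-over at the skin step. This stands: a reader might infer that the rater is picked after allocation, but the documents only leave that open.

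A reader might also infer that the primary outcome is compromised in the same way. It is not. SBSES is scored by the attending who performed the procedure, whoever closed the skin, so the rater-selection argument does not reach it. Only an unquantified effect of closer skill on the scar remains.

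Nor may one infer that the bias would favour the devices. Every input to its size is assumed, and its direction can go either way.

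It can further be said that if a device lets a different grade close, that is a real consequence of the device. This is partly a choice of question. However, the Background asks for the time each method requires, the training is meant to make experience uniform, and the cost formula has no staff-grade term. All three point to comparing techniques with the operator held comparable.

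Finally, the clinicians are a defined group of 10 and the closer completes the survey, so grade may be recoverable. The documents do not say that it is recorded, and recovering it later would not show who had been intended before opening.

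**Conclusion.** The gap is real and of minor severity. The plan permits the skin closer, and with that the satisfaction rater, to be settled with knowledge of the arm, and its safeguards do not close that route. The outcomes mainly exposed are physician satisfaction, closure time and cost, all secondary.

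The documents do not show that selection will occur. The differences of 0.6 and 1.2, and the false-positive rates of 6 to 27% at 10 per arm, rest wholly on assumed grade effects and closer shares. They show what could happen, not what is expected. If grade mix does not depend on the arm, the ANOVA keeps its nominal 5%.

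**What to change.** In Study Procedures, item 1:
- Before the envelope is opened, the circulator records the intended skin closer's study code and grade on the envelope or form.
- That person does the skin step in whichever arm is drawn, and any change of closer is recorded with its reason.

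In Statistical Considerations, item 5: tabulate closer grade by arm beside satisfaction, closure time and cost.

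The cost is one line on a form, a sentence or two of protocol text and one table, with slightly less staffing flexibility just before closure. The change does not remove chance imbalance in grade, which the table would at least make visible, and the satisfaction rating remains unblinded. It has to be made prospectively, because the intended closer cannot be reconstructed once the operations are done.

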# 2. What are the statistical considerations for the protocol?

Primary outcome variable: SBSES scores will be assessed at scheduled post operative visits. The minimal clinically important difference will be defined as 1 point. The null hypothesis is that

there will be no difference between the SBSES scores between treatment groups (one-way ANOVA).

Secondary outcome variables: patient satisfaction with appearance of scar (on scale of 1-10), physician satisfaction with the technique/device (on a scale of 1-10), and presence or absence of adverse events (including infection and reoperation). For the scaled scores, descriptive statistics will be calculated, and means between groups will be compared (one-way ANOVA). A count of the adverse events per group will be tallied.

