A brief survey will then be completed by the study participant to rate their satisfaction with their surgical scar on a 1 - 10 scale. The physician or physician assistant seeing the subject in follow up will document the presence or absence of adverse events (including infection and reoperation).

The SBSES assessment, adverse event monitoring and patient satisfaction will be recorded at a second standard of care follow up visit between 10 - 14 weeks after surgery. The subject will be released from the study after the final standard of care follow up visit occurs, and will no longer need surveillance or monitoring.

Cost analysis between the groups will be assessed using the above statistical approach. To carry out this analysis, we will obtain: 1. Cost for all materials needed for wound closure, 2. Amount of time (in minutes and seconds) needed to close the wound (start time = all supplies are gathered to close the wound, and stop time = wound is declared fully closed), and 3. Operating room costs (including overhead) per minute.

Version Date: 07-29-22 Page Number: 6 of 8

2. If this protocol involves study treatment, explain how a subject will be transitioned from study treatment when they have completed their participation in the study.

The patients that are involved in the study treatment groups will have the same post operative management as the control group. At the 2 week visit, the devices (Clozex or Zipline) will be removed and all groups will have the same wound care instructions.

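### At the first follow-up the unblinded operating surgeon scores the scar before the patient rates it, so the surgeon's reaction may influence the patient's satisfaction rating

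*Combined protocol and SAP*

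**What the plan says.** The sequence for the first follow-up, 14 to 17 days after surgery, is in Study Procedures-Biomedical Research, item 1.

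- Closure material comes off: "at which point Prolene sutures will be cut and removed and Clozex/Zipline devices will be removed".
- The SBSES is scored: "An assessment of the wound will take place by the same attending surgeon who performed the procedure".
- The patient rates the scar, from 1 to 10: "A brief survey will then be completed by the study participant to rate their satisfaction with their surgical scar".

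For the visit at 10 to 14 weeks, the same item lists the measures without giving a sequence: "The SBSES assessment, adverse event monitoring and patient satisfaction will be recorded at a second standard of care follow up visit".

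Statistical Considerations, item 1, states: "There will be no blinding of subjects or personnel involved in the study once the envelope with group assignment has been opened". Study Procedures, item 1, adds: "The clinicians performing the closure are also investigators in this research".

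Patient satisfaction is a secondary outcome, compared across the three groups by one-way ANOVA (Statistical Considerations, items 2 and 5). It is also named in the null hypothesis under Objectives/Hypothesis. No section has the patient rate first, rate in private, or be kept apart from the surgeon's assessment.

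**The concern.** The surgeon knows which closure was used, performed the operation, and may be an investigator with a view on the devices. The last SBSES item asks the surgeon for an overall judgement of the scar as good or poor. The patient is then asked about much the same thing, satisfaction with how the scar looks. A remark or a visible reaction during scoring reaches the patient before the patient answers, and it could differ by arm.

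If that happens, a clinician's preference for or against a device enters a second endpoint. A difference between arms in patient satisfaction could then partly reflect the surgeon's opinion, and the collected data would give no means of separating the two.

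**Working it through.** **1. The plan's own figure.** The only design calculation is for the SBSES (Statistical Considerations, item 3): SD 0.73, difference 1 point, alpha 0.05, power 0.80, giving 10 per group.

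- A two-sample t-test (noncentral t) gives 10.
- For a three-group ANOVA, the noncentrality is λ = n × SS / SD², where SS is the sum of squared deviations of the group means.
- If one group differs from two equal groups, SS = 2/3 and 9 per group suffice.
- If the third mean lies midway, SS = 1/2 and 12 are needed.

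The stated 10 is reproduced within 2 patients. This point does not depend on it, and changing the order of ratings alters none of its inputs.

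**2. The order, visit by visit.**

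| Visit | Surgeon's SBSES | Patient's rating | Order |
|---|---|---|---|
| Day 14-17 | After removal of sutures or device | After the SBSES | Explicit |
| 10-14 weeks | Recorded | Recorded | Not stated |

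The order is therefore established for the first visit only.

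**3. What a carry-over could do to the ANOVA.** The documents give neither an SD for the 1-10 rating nor any estimate of carry-over, so both are assumed here.

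- From the plan: 3 groups, and 10 analysed per group (up to 20 enrolled). The plan states alpha 0.05 for the SBSES sample size; it is applied here to satisfaction.
- Assumed: SD s = 1.5, 2 or 2.5; no true difference between arms; the same shift b in both device arms, so the group means are 0, b, b.

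The sum of squared deviations is (2b/3)² + 2(b/3)² = 2b²/3, so λ = n × (2b²/3) / s². The rejection probability is the chance that a noncentral F with 2 and 3(n − 1) degrees of freedom exceeds the central 95% point.

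Example: for n = 10, s = 2 and b = 1, λ = 10 × (2/3) / 4 = 1.667. The degrees of freedom are 2 and 27, the critical value is 3.354, and the rejection probability is 17.8%.

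| Shift b | n = 10: s = 2.5 | s = 2 | s = 1.5 | n = 20: s = 2.5 | s = 2 | s = 1.5 |
|---|---|---|---|---|---|---|
| 0 | 5% | 5% | 5% | 5% | 5% | 5% |
| 0.25 | 5.5% | 5.7% | 6.3% | 6.0% | 6.5% | 7.7% |
| 0.5 | 6.8% | 7.9% | 10.3% | 9.0% | 11.4% | 17.0% |
| 1 | 12.9% | 17.8% | 28.8% | 22.8% | 33.7% | 55.5% |

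A quarter-point carry-over would hardly matter at 10 per arm. A full point would.

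**The case against.** The strongest reply is that the documents show an opportunity for influence, not influence itself. No section says that the surgeon voices a score, shows a reaction, or is present while the survey is completed. A reader might infer that patient satisfaction is simply an echo of the surgeon's view; the text supports only that it may be affected. This stands.

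Other parts of the reply also stand:

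- **Second visit.** A reader might infer that the surgeon goes first at both visits. The later visit has no stated sequence, and the plan does not say which visit supplies the analysed satisfaction score.
- **Partial remedy.** Patients know their arm and change their own dressings after day 3, so many may already have a view of the wound. A clinician may also comment while removing the closure material. Reordering addresses only the surgeon's influence during scoring.
- **Hypothetical size.** The larger percentages could be taken as estimates of bias. They rest on an assumed SD and an assumed shift, equal and in the same direction in both device arms. With up to 10 clinicians, preferences might differ and partly cancel, or favour one device.
- **No planned corroboration.** A reader might fear that agreement between the SBSES and satisfaction will be presented as independent confirmation. The plan has separate ANOVAs and no analysis linking the two.
- **Reversal is not free.** If the surgeon sees the patient's rating first, it could influence the SBSES, which is the primary outcome. The documents also name no non-operating staff to hand out the form.

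None of this is a reason to keep the present order, for which the documents give no rationale. It does limit the strength of the claim, and it means that the completed form must be concealed from the surgeon.

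**Conclusion.** The point holds as a minor design weakness. At the day 14-17 visit the written procedure puts an unblinded operating surgeon's assessment directly before the patient's rating, with nothing to separate them. That leaves an avoidable route for bias into one secondary outcome. At 10-14 weeks the gap is an unstated order, not a wrong one.

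The documents do not allow the effect to be sized. Under the assumptions above it runs, at 10 per arm, from negligible (5.5-6.3% false positives for a 0.25-point shift) to material (13-29% for a full point). The conclusion rests on the stated sequence and the absence of blinding, not on those percentages. The unblinded surgeon's scoring of the primary outcome is a larger matter, and this change does not touch it.

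**What to change.** In Study Procedures-Biomedical Research, item 1, where the follow-up visits are described, state for both visits that:

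- once the dressing and any closure material are off and the scar is visible, the participant completes the 1-10 survey before the surgeon scores the SBSES or comments on the scar; and
- the completed form is kept from the surgeon until the SBSES has been recorded.

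The cost is a sentence or two of protocol text and a small change to visit flow and form handling by existing clinic staff. No visit, measure, patient or analysis is added, and sample size, alpha and power are unchanged. The change should be made before ratings are collected, because any carry-over cannot be removed from them afterwards.

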Our primary objective outcome measure will be an assessment of surgical scar characteristics using the Stony Brook Scar Evaluation Scale (SBSES) which has been validated in the assessment of surgical scars in the first year after surgery. Secondary outcome measures will include adverse events related to the surgical wound, surgical time for closure, a patient satisfaction score and physician satisfaction score.

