# 5. What is your plan for secondary variable analysis?

Secondary outcome variables: patient satisfaction with appearance of scar (on scale of 1-10), physician satisfaction with the technique/device (on a scale of 1-10), and presence or absence of adverse events (including infection and reoperation). For the scaled scores, descriptive statistics will be calculated, and means between groups will be compared (one-way ANOVA). A count of the adverse events per group will be tallied.

Cost analysis between approaches will be assessed using the following metrics: the cost of operating room time per minute will be multiplied by the time for closure and added to the cost of materials to determine a total cost for each approach. The average costs for each approach will be compared using a one-way ANOVA to determine if there are significant differences in costs.

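### Closure time has two possible start points and no named test, and the cost comparison ignores incision length, so the secondary speed and cost results are less precise than they could be

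*Combined protocol and SAP*

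**What the plan says.** **Start and stop of the clock.** Study Procedures, question 1, lists deep fascia (step 1) and subcutaneous fat (step 2), both closed the same way in every arm. Step 3 follows: "The circulator will then start a timer that will run until the wound is completely closed". Step 5 ends it: "At the conclusion of the wound closure, the timer will be stopped and the operative time will be recorded". The cost paragraph later in the same answer gives its own definition: "start time = all supplies are gathered to close the wound, and stop time = wound is declared fully closed". That paragraph names no tissue layer, and its materials item is "Cost for all materials needed for wound closure".

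**When supplies are gathered.** The allocation envelope is opened during surgery, before closure starts. The stated purpose is: "This will allow operating room staff the time to assemble the appropriate materials for closure".

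**Outcome and test.** The Background states: "Secondary outcome measures will include adverse events related to the surgical wound, surgical time for closure". The Objectives also list surgical time. Statistical Considerations, questions 2 and 5, omit it from the secondary outcomes and name ANOVA only for the 1–10 scores and for cost. Cost is operating-room rate times closure time plus materials, and "The average costs for each approach will be compared using a one-way ANOVA".

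**Incision length.** Eligibility requires a "minimum anticipated incision length of 3 cm" and sets no maximum. Randomization is not stratified. The closure survey asks for notes on a difficult incision pattern but does not record length.

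**The concern.** Two timing rules for one quantity mean that a circulator or data abstractor has to choose. If the supplies-gathered start is used and the supplies are ready before step 1, the measured time includes two layers that do not differ by arm. Those layers raise the absolute cost in every arm and add variation unrelated to the skin-closure method. Applied uniformly, this does not bias the difference between arms, but it makes a real saving harder to see.

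Incision length matters for a similar reason. A long incision plausibly takes longer to close by any method. With no upper limit on length, variation between procedures goes straight into the error term of an unadjusted comparison. Length not written down in theatre has no other source in the protocol.

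Speed and cost are stated aims of the trial, and both rest on this one measurement.

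**Working it through.** **The texts side by side**

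| Place | Clock starts | Layers timed |
|---|---|---|
| Study Procedures, question 1, step 3 | after fascia and fat are closed | skin only |
| Study Procedures, question 1, cost paragraph | when closure supplies are gathered | not stated: skin only, or fascia, fat and skin |

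The protocol counts fascia and fat closure as steps of the wound closure, and its description of the control closure also includes the deeper layers. The all-layers reading is therefore open. The skin-only reading is open too, and the text does not choose.

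**Inputs**

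- Three arms, equal allocation, alpha 0.05 (Statistical Considerations, questions 1 and 3; Study Procedures, question 1).
- n per group: 10 for analysis, up to 20 enrolled (Statistical Considerations, question 3). Time is recorded in theatre before any loss to follow-up, so n may be nearer 20. Both are shown.
- The plan states no SD, effect or sample size for time or cost, so it has no figure of its own to reproduce here. Its 10 per group is for SBSES.
- Assumed: both devices are d = 1 SD faster than control, where the SD is that of skin-step time.

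**Formula.** With means (0, d, d), the noncentrality is λ = n × (2/3) × d² / σ². Power is the probability that a noncentral F with 2 and 3n − 3 df exceeds its 5% critical value. ANCOVA uses 3n − 4 df.

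**Base case, σ = 1.** For n = 10, λ = 10 × 2/3 = 6.67 and power is 58.1%. For n = 20, λ = 13.33 and power is 90.0%.

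**Adjusting for length.** σ² = 1 − R², where R² is the share of variance explained by length.

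| R² | n = 10 | n = 20 |
|---|---|---|
| 0 | 57.9% | 89.9% |
| 0.09 | 62.2% | 92.6% |
| 0.3 | 74.4% | 97.5% |
| 0.5 | 87.9% | 99.7% |
| 0.7 | 98.4% | 100.0% |

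Example: at R² = 0.5 and n = 10, λ = 6.67 / 0.5 = 13.33. The formula ignores chance imbalance in length, so it is slightly optimistic. Simulation at n = 10 gave 86.5% for correlation 0.7 (R² = 0.49), and a loss of about 1 point when length is irrelevant. Type I error stayed near 5% with and without adjustment.

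**Including the deeper layers, unadjusted.** Let their SD be r times the skin-step SD, with correlation ρ between the two. Then σ² = 1 + r² + 2ρr.

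| ρ | r | σ | n = 10 | n = 20 |
|---|---|---|---|---|
| 0 | 0.5 | 1.118 | 48.4% | 82.0% |
| 0 | 1 | 1.414 | 32.0% | 60.8% |
| 0 | 2 | 2.236 | 15.0% | 27.6% |
| 0.5 | 1 | 1.732 | 22.5% | 43.5% |
| 0.5 | 2 | 2.646 | 12.0% | 20.7% |

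**Unequal slopes.** A device may save time per centimetre, which breaks the common-slope assumption. Simulation (40,000 runs) set the device slope at half the suture slope, with a 1 SD saving at mean length. Control-arm R² was 0.3, 0.5 and 0.7.

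| n | Common-slope ANCOVA | Unadjusted |
|---|---|---|
| 10 | 71.4 / 84.0 / 95.9% | 64.6 / 69.1 / 74.2% |
| 20 | 96.9 / 99.4 / 100.0% | 93.5 / 95.3 / 96.9% |

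ANCOVA type I error was 4.9% to 5.3%.

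**The case against.** The strongest reply is that only one timer is described. Step 3 starts it and step 5 stops it, and the cost paragraph may simply be shorthand for the same interval. On that reading the conflict is loose wording. The unadjusted ANOVA is valid, so adding length is an optional gain whose size depends on a correlation the documents do not give. Gains are small if that correlation is weak (58% to 62% at R² = 0.09, n = 10). They are limited if n is near 20, where power starts at 90%. They also shrink if the effect is large: at d = 1.5, unadjusted power is already 92% (n = 10) or 99.9% (n = 20). Unequal slopes reduce the gain to about 3 to 4 points at n = 20. The missing test could be read across from the ANOVA named for the other continuous outcomes.

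Much of this stands as a limit on size. The two starts may coincide in practice, and the trial's error rate is not at risk. What it does not answer is that nothing in the text makes the starts coincide, that a declared outcome has no stated analysis, and that length will not be recorded. In the scenarios examined, adjustment costs at most about 1 point of power when length is irrelevant and gains power when it matters.

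**Conclusion.** The point holds as a low-cost improvement to secondary outcomes. The two start definitions, the missing test and the absent length variable are established from the text. The size of the precision loss is not, because it rests on an assumed 1 SD saving and assumed variances and correlations. Over R² from 0.3 to 0.7, adjustment takes power from 58% to between 74% and 98% at n = 10, and from 90% to between 97.5% and nearly 100% at n = 20. Including deeper layers with one to two times the skin-step SD would cut unadjusted power to 12–32% at n = 10 and 21–61% at n = 20.

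Uniform use of either start leaves the arm differences unbiased. Bias would arise only if the chosen start varied by arm. That is possible, since theatre staff are unblinded once the envelope is opened, but nothing in the plan shows it. The SBSES analysis is unaffected.

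**What to change.** 1. In Study Procedures, question 1, use a single start event in both places: step 2 complete and skin closure beginning. Keep the step 5 stop, and state that this is the time used in the cost formula.
2. Add incision length in centimetres to the closure form. The incision exists before allocation is revealed, so length is a legitimate baseline covariate. It is best measured before the envelope is opened.
3. In Statistical Considerations, question 5, list closure time as a secondary outcome with its test. Analyse closure time and cost by ANCOVA with arm and incision length, replacing the unadjusted ANOVA for cost.
4. Report the arm-by-length interaction descriptively, as a check on the common-slope assumption.

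The cost is one sentence of definition, one recorded number per patient and one degree of freedom. The drawback is the common-slope assumption. In the unequal-slope scenario examined, ANCOVA kept its error rate near 5% and still had more power than the unadjusted test.
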